**Aim 1. Create a group navigation model to improve mental and emotional health equity for Spanish-speaking Latina women.** In a series of peer group sessions facilitated by [name], a CHW who designed the model, we will create a culturally-appropriate, non-stigmatizing group intervention. The group process will allow participants to explore their own MEH, better understand the ways that mental health influences well-being and everyday dynamics of their lives, and to develop empowering knowledge and action plans through the support of other women. We will document group discussions, processes, and themes, gather information about women's explanatory models of MEH, and administer a multidimensional survey to capture information about the domains of interest. Through individual case management, [name] will work individually with women from the groups to identify their specific social and structural determinants needs, assist them to make an individual action plan, provide them with information about available resources, and help them navigate systems and access resources and services. We will document participant needs and navigation outcomes. **Hypotheses:** Participation will decrease depression, social isolation, and social determinants needs, and increase emotional support, informational support, and women's sense of empowerment.

**Aim 2. Create an advocacy plan.** With data gathered in group meetings and individual navigation sessions, we will identify social and structural barriers that negatively influence participants' MEH outcomes and ability to access resources and services. We will create an advocacy plan to address structural and policy barriers that can be implemented by CHWs and advocacy groups in the future. **Hypotheses:** We can identify factors that negatively influence the MEH and well-being of Latinas. We hypothesize that in the future, we can use this knowledge to develop a strategic plan with the potential to address socio-structural and policy barriers through advocacy.

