**Aim 3. Assess the feasibility of the intervention.** We will track recruitment, attrition, attendance at group sessions, and attendance at individual CHW navigation meetings. We will gather survey data and qualitative data to document participant experiences with and perceptions of the group process, working with the CHW, and the value of the intervention. **Hypotheses:** The intervention we pilot will be feasible, acceptable, valuable, and culturally appropriate.

**Expected Outcome.** This pilot study will use team science to test an intervention that emerged organically in the community and contribute to building the next generation of health disparities research using knowledge generated through solution-based investigation as the foundation for submitting an NIH R21 research proposal.

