## Significance

Latina MEH Disparities: New Mexico (NM) is one of five majority-minority states with 48% of the population identifying as Hispanic, a group that experiences poor health outcomes. Moreover, there is evidence of an “immigrant paradox” or “nativity effect,” wherein recent immigrants experience mental and emotional health (MEH) disorders at lower rates than native born Hispanics. However, others have cautioned that Hispanics/Latinos are not a monolithic group even within the immigrant community.

More recent research has shown that social-structural conditions negatively influence the health of the immigrant population, with significant disparities in the realm of MEH. In particular, providers in Albuquerque’s International District have identified MEH as a significant concern among Spanish-speaking Hispanic women (Latinas), especially those from the Mexican immigrant community.

Through our research and community work with this population, members of our team have found that Latinas often: 1) misrecognize MEH symptoms and are unsure how they can be addressed through existing community resources, 2) require assistance identifying and navigating systems and services, 3) lack social and emotional support, and 4) experience personal disempowerment.

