### **Approach**

Theoretical Model: The model in the study is informed by **socioecological approaches** to address disparities and affect change at **multiple levels** as broadly constructed by a **social and structural determinants of health framework.** We included attention to change at the level of the individual, the social group, and external infrastructure (e.g. political, legal, economic and other social/institutional factors). Our pilot addressed social and structural determinants at each of these levels.

Research Design: We use a **convergent parallel mixed method research design** to implement an intervention to affect **six domains of interest** in the lives of Latinas: 1) emotional support, 2) informational support, 3) depression, 4) social isolation, 5) empowerment, and 6) social determinants needs. Further, we will assess the feasibility of implementing this model with 30 participants. The intervention integrated navigation assistance and case management by a CHW with a peer support group. We gathered both qualitative and quantitative data using a variety of instruments and methods as described below, and we will integrate different types of data during analysis and interpretation.

Team Expertise & Roles: Our transdisciplinary team integrated expertise from anthropology, community-engaged research, social work, counseling, community navigation, and biostatistics, and we are well situated to conduct the proposed research. **[name] [name], the PI**, is a cultural anthropologist and Research Assistant Professor of Pediatrics in the Prevention Research Center. She has over 20 years’ experience conducting community-engaged research with migrants and other marginalized people to improve health and well-being. **[name], Principal Community Mentor and Co-Investigator**, was trained as a Special Education teacher in Aguascalientes, Mexico and

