**Population:** This project involved Spanish-speaking Latinas from low-income households. Participants was recruited from the International District and South Valley neighborhoods of Albuquerque and screened for language, self-reported ethnic identity as Latino/Hispanic, and self-reported income below 250% of the Federal Poverty Level. The majority of the participants were Mexican immigrants with one participant who was from Central America and one who was a second generation Mexican immigrant.

**Recruitment:** During month #2 prior to the start of the intervention, [name] recruited 30 participants through the Pathways Program, the Simplemente Salud Clinic and Centro Sávila. In the course of regular meetings with clients who request a range of services, she identified identify and invite those who might benefit from the proposed model. While participants experessed interest int eh program, lower numbers than anticipated joined the study from the first 3 cohort. We therefore changed the implementation strategy to allow for two sequential cohorts, one in the Fall and and one in the Spring.

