#### Intervention Implementation:

**MONTH #1:** Planning, logistics, & preparation.

**MONTH #2:** Recruitment.

**MONTH #3:** During month #3, each cohort of 10 participants participated in four two-hour classes held weekly and facilitated by [name] with assistance from [name]. Class 1 included introductions and open-ended discussion of participants' perspectives on and experiences with MEH challenges including eliciting explanatory models of illness using a structured dialogue approach. In Class 2, [name] presented information on concepts of MEH including anxiety, depression, and social isolation, and the group explored ways that participants' own experience may align with these concepts. In Class 3 participants identified and give name to their feelings and experiences and begin to consider services they might be interested in accessing. In Class 4, [name] provided information about relevant health care and other resources, for example, school counselors, domestic violence services, Centro Sávila, The Hopkins Center, couples counseling, UNM mental health services/counseling, and church support groups.

**MONTH #4:** Over the first three weeks of month #4 of the intervention, the team conducted a preliminary analysis of class notes, observations and audio (described in the data analysis section below) to identify common themes and specific resource and service needs for each participant, and in week 4 of month #4, reconvene the groups for Class 5 to discuss findings and individual experiences with accessing resources and services since Class 4 and individual participants will develop action plans.

**MONTHS #5-7:** [name] provided individual case management to assist participants to access resources and navigate systems to achieve goals identified in their individual action plans.

**MONTH #8:** We reconvened the groups for Class 6 to engage in a follow-up discussion of outcomes and to administer the post-survey.

Mixed method data collection.

| Construct                | Instrument              | # of Items | Time point |
|--------------------------|-------------------------|------------|------------|
| Demographic Info         |                         | 18 items   | B only     |
| Depression               | PHQ-9                   | 9 items    | B&F        |
| Emotional Support        | PROMIS  | 8 items    | B&F        |
| Informational Support    | PROMIS     | 8 items    | B&F        |

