## Results

Intervention was acceptable and feasible. Increase in resiliency was our most robust quantitative finding. Social, emotional and informational empowerment scores improved, but not in statistically significant way. Depression scores worsened, which could reflect the effectiveness of the psychoeducation component. Qualitative results: participants' experiences in the intervention underscored the importance of recognizing cultural differences in values and meaning related to MEH: 1) Self-advocacy and self-efficacy (learning how to say "no" or set limits as Latinas) ; 2) Addressing violence (in domestic settings, in families, social violence) ; 3) Isolation and socializing (recognizing differences in U.S. v. Latin America) . Overall, the results demonstrated the importance of multilevel interventions that address mental health at multiple levels: 1) Individual:

| Research Timeline                                | Month |   |   |   |   |   |   |   |   |    |    |    |
|--|-------|---|---|---|---|---|---|---|---|----|----|----|
|  | 1     | 2 | 3 | 4 | 5 | 6 | 7 | 8 | 9 | 10 | 11 | 12 |
| Activity   |       |   |   |   |   |   |   |   |   |    |    |    |
| Planning/Logistics                               | ■     |   |   |   |   |   |   |   |   |    |    |    |
| Recruitment                                      |       | ■ |   |   |   |   |   |   |   |    |    |    |
| Cohort 1 (Classes 1-4)                           |       |   | ■ |   |   |   |   |   |   |    |    |    |
| Quantitative Baseline Interview                  |       |   |   |   |   |   |   |   |   |    |    |    |
| Cohort 2 (Classes 1-4)                           |       |   |   | ■ |   |   |   |   |   |    |    |    |
| Cohort 3 (Classes 1-4)                           |       |   |   |   | ■ |   |   |   |   |    |    |    |
| Analysis of Class Data                           |       |   |   |   | ■ | ■ |   |   |   |    |    |    |
| Class 5 – Discuss Findings, Resource Access Plan |       |   |   |   |   | ■ | ■ |   |   |    |    |    |
| Individual Case Management                       |       |   |   |   |   |   | ■ | ■ | ■ |    |    |    |
| Class 6 – Follow-up to Discuss Outcomes          |       |   |   |   |   |   |   |   | ■ |    |    |    |
| Quantitative post-interview                      |       |   |   |   |   |   |   |   |   | ■  |    |    |
| Data Analysis of Outcome Class                   |       |   |   |   |   |   |   |   |   | ■  | ■  |    |

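### Worsened depression scores receive only a favourable explanation, and the Aim 1 depression hypothesis is never said to be unsupported

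*Combined protocol and SAP*

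**What the plan says.** The Aim 1 hypothesis in Specific Aims gives a direction in advance: "Participation will decrease depression, social isolation, and social determinants needs". Depression is one of the six target domains, and the data collection table assigns it to the PHQ-9 at baseline and follow-up.

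Under Intervention Implementation, the second class "presented information on concepts of MEH including anxiety, depression, and social isolation". Baseline was taken at Class 1, so this teaching came after it. For follow-up, the Month #8 entry reads "We reconvened the groups for Class 6 to engage in a follow-up discussion of outcomes and to administer the post-survey".

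The Quantitative analysis paragraph says that means with 95% CIs were reported at both time points and for the changes.

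On depression, the Results section says only this: "Depression scores worsened, which could reflect the effectiveness of the psychoeducation component". The sentence just before it states that the improvements in the social, emotional and informational scores did not reach statistical significance. The depression sentence has no such statement. Conclusions do not return to the depression scores. The limitations named there concern recruitment, payment bureaucracy and completing surveys in class.

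**The concern.** A domain with a pre-stated direction moved the other way, and the only reading offered is that the intervention worked. None of the text available for review predicts that teaching about depression would raise the scores, so the explanation is post hoc. If a fall was the predicted benefit and a rise is also read as effectiveness, either direction counts as success.

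The pilot is intended "as the foundation for submitting an NIH R21 research proposal". Whoever plans that study needs to know three things: that one of six domains went against its hypothesis, by how much and with what uncertainty, and that the surveys do not show why. True worsening is the alternative that a mental-health intervention most needs to name, and the text does not name it.

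**Working it through.** **The passages side by side**

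- Predicted (Aim 1): depression decreases. Observed (Results): depression worsens. Neither Results nor Conclusions states that the hypothesis was not supported.
- Planned for reporting (Quantitative analysis): mean change and 95% CI. Given in Results: direction only.
- Design: one group, surveyed at Class 1 and Class 6. The text available for review describes no comparison group. The instrument table has no measure of symptom recognition.

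With only two PHQ-9 readings per woman and no comparison group, a higher mean at follow-up could come from five sources: better recognition, chance, true worsening, change over time, or loss of women whose scores would have moved differently. All five look the same in these data. I assume no particular follow-up month, because Intervention Implementation puts Class 6 and the post-survey in month 8, while the Research Timeline puts Class 6 in month 9 and the post-interview in month 10.

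**The plan's own figure**

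Inputs from Quantitative analysis: n=30, alpha 0.05, power 0.80, d=0.53. Sidedness is not stated. A two-sided paired t-test (noncentral t) with n=30 and d=0.53 gives power 0.801, and the smallest detectable d at 80% power is 0.529. The stated figure reproduces. A one-sided test would give power 0.883, so the plan's figure is two-sided.

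**Can chance be set aside?**

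The number analysed is not given. Recruitment says that 30 women were recruited but also that "lower numbers than anticipated joined the study", so I show n=30 and, as assumptions, n=20, 15 and 10. Everything is in units of the SD of the change score.

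- 95% CI half-width = t(0.975, n−1)/√n. At n=30: 2.045/5.477 = 0.373.
- Probability that the observed mean worsens when the true improvement is d: 1 − Φ(d√n). At d=0.2, n=30: 1 − Φ(1.095) = 0.137. The values of d are assumptions.

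| n | CI half-width | Detectable d (80% power) | P(worsens), d=0 | d=0.1 | d=0.2 | d=0.3 |
|---|---|---|---|---|---|---|
| 30 | 0.37 | 0.53 | 50% | 29% | 14% | 5% |
| 20 | 0.47 | 0.66 | 50% | 33% | 19% | 9% |
| 15 | 0.55 | 0.78 | 50% | 35% | 22% | 12% |
| 10 | 0.72 | 1.00 | 50% | 38% | 26% | 17% |

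An observed worsening smaller than the half-width has a 95% CI that includes no change. A statement of direction alone therefore does not tell the reader whether this is noise or deterioration.

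**The case against.** The strongest case for leaving the text alone has four parts.

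**The result is disclosed and hedged.** The word used is that scores worsened, the explanation is introduced with a conditional, and Conclusions call the results preliminary and claim no benefit on depression. A reader who compares Aim 1 with Results can see the conflict. No other hypothesis receives a formal verdict either. This is fair, but hedging one favourable reading does not do the work of naming the unfavourable ones.

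**The recognition reading has support.** Significance says that Latinas often "misrecognize MEH symptoms and are unsure how they can be addressed through existing community resources", the teaching on depression came after baseline, and the qualitative themes in Results include emotional awareness and how common depression and anxiety are. The study is a "convergent parallel mixed method research design", so the surveys were not meant to stand alone. All of this makes the reading plausible and worth keeping. Nothing in the documents links those themes to PHQ-9 change, so it remains untested.

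**Missing estimates are general.** Results give no estimate, interval or n for any outcome, and a separate final report is listed that may contain them. That stands. What is particular to depression is that its neighbours have a significance status and it does not.

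**The magnitudes rest on assumptions.** The smaller n and the true effects are not in the documents, and the 50% figure holds for any null change. Selective follow-up is only a possibility, because no attrition figure is given. This is correct: the figures show that chance is possible, not how large the error is. The argument does not need the smaller n, since at n=30 the half-width is already 0.37 SD.

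**Conclusion.** The concern holds. The Results section gives only a favourable post hoc explanation for a change that runs against a pre-stated hypothesis, and the document never says that the hypothesis was unsupported. The uncontrolled pre/post surveys cannot distinguish that explanation from chance, true worsening, change over time or selective follow-up.

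The size of the depression change is unknown from these documents. Its uncertainty would be about ±0.37 SD of change at the planned n, and wider if fewer women were analysed. This is a defect of interpretation and reporting; the sample-size arithmetic is sound, and nothing here shows that harm occurred. The absence of a comparison group is judged from the text available, because some pages were removed before review. The text should be corrected before it is used to support the next proposal.

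**What to change.** In Results, replace the depression sentence with wording such as:

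> PHQ-9 scores worsened from baseline to follow-up (mean change, 95% CI, number with both surveys). The Aim 1 hypothesis that depression would decrease was not supported. Greater symptom recognition after psychoeducation is one untested, post hoc explanation; chance, true worsening, change over time and selective follow-up are others, and the uncontrolled pre/post surveys cannot separate them.

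If the recognition reading is kept, cite the qualitative themes as compatible with it and say that they were not linked to PHQ-9 change. In Conclusions, add the absence of a comparison group to the limitations.

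Optionally, show baseline PHQ-9 for women with and without follow-up. This is description only: it shows who was lost, not whether their change would have differed.

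The cost is a few sentences and one estimate that the Quantitative analysis paragraph already specifies. The optional comparison uses data already in REDCap. The only downside is a less favourable statement of the depression result.

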### **Conclusions**

The study showed that interventions designed by community members effectively address barriers to addressing MEH (sociocultural attitudes and responses to MEH, current context and effects on Latinas). The research broadened our understanding of how MEH is impacted by sociocultural, economic, and policy-level factors is necessary to create effective interventions for addressing MEH. Preliminary results offer insight into how multilevel change is needed to improve mental health equity.

The recruitment process showed that potential participants recognized a great need for such interventions among Spanish-speaking Latinas, but stigma, as well as family and work obligations made it difficult for women to commit to the class at the outset. However, the benefits of attending the class have spread by word of mouth, if funding were to be found for continued intervention, it is certain that there would be robust participation. Another major limitation for this project and community-based work generally were the bureaucratic barriers/mismatch between the university and the community-based organizations to ensure timely payment for the organization. Additionally, survey completion during class was a barrier. In the future, a plan to collect baseline and follow-up data in person would make the first session flow better and be less intimidating for participants.

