| Social Isolation         | PROMIS     | 8 items    | B&F        |
| Resiliency               | CD-RISC                 | 25 items   | B&F        |
| Adverse Childhood Events | ACES                    | 10 items   | F          |
| ACES Resiliency          | ACES + Resiliency       | 12 items   | B&F        |
| Eval & Feasibility       |                         | 8 items    | F          |

*Quantitative data collection:* Data was stored in a database created in UNM's secure data capture system, REDCap. We tracked recruitment, attrition, attendance at group sessions, and attendance at individual CHW navigation meetings. Pre-/Post-data was gathered at baseline (Class 1) and follow-up (Class 6) in the form of a multi-dimensional survey (see table). The survey will include: A) demographic questions to characterize participants, B) program evaluation/feasibility questions to document participant experiences with and perceptions of the group process, working with the CHW, and the value of the intervention, C) seven reliable instruments that have been validated in English and Spanish to measure the six domains of interest: a) emotional support, b) informational support, c) social isolation ; d) depression; e) ACES; and f) resiliency.

*Qualitative data collection:* Group class sessions were audio-recorded. [name] and/or [name] attended Classes 1 and 6 for each cohort and take observational notes. Analytical notes taken during team meetings. Notes from individual case management sessions, individual resource action plans, and the Advocacy Plan will be documented and analyzed.

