#### Data Analysis

*Quantitative analysis:* Descriptive statistics were presented for baseline participant characteristics: means and standard deviations or medians and quartiles for continuous measures, and frequencies and percentages for categorical measures. All instrument measures at baseline and follow-up were summarized with appropriate descriptive statistics. The seven quantitative measures from the PHQ-9, PROMIS support instruments, and PPS-R were reported as unadjusted mean scores and their 95% confidence intervals (CIs) at each of baseline and follow-up, as well as for the changes from baseline to follow-up. We predicted with a sample size of 30, we would be able to detect medium effect sizes (Cohen's  $d=0.53$ ) of instrument change scores between the two time points (unadjusted type I error rate  $\alpha=0.05$ , power  $1-\beta=0.80$ ). SAS 9.4 will be used for all statistical analyses.

*Qualitative analysis:* We employed a constructivist grounded theory approach which is a well-known way to explicate processes, in this case change related to the intervention. Theory is "grounded" in the data themselves. Constructivist grounded theory therefore uses a combined inductive

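### The Conclusions call robust future participation certain, but no recruitment counts are reported and no data source in the plan measures demand

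*Combined protocol and SAP*

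**What the plan says.** Aim 3 (Specific Aims) lists recruitment first among the things to be tracked for feasibility, and the quantitative data collection paragraph confirms that it was tracked. The Approach sets the scale: "we will assess the feasibility of implementing this model with 30 participants".

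The Recruitment paragraph says that the recruiter enrolled 30 women whom she met through her regular client meetings, and that women showed interest. It then says "lower numbers than anticipated joined the study from the first 3 cohort", and that the plan was changed for this reason to two sequential cohorts, Fall and Spring.

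Survey data start with the first class: "Pre-/Post-data was gathered at baseline (Class 1) and follow-up (Class 6) in the form of a multi-dimensional survey". The instrument table places demographics at baseline only and the evaluation and feasibility items at follow-up only.

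The Conclusions, drawing on the recruitment process, report that "stigma, as well as family and work obligations made it difficult for women to commit to the class at the outset". They then turn to word of mouth and state that "if funding were to be found for continued intervention, it is certain that there would be robust participation".

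**The concern.** Certainty about uptake is a strong statement for a pilot whose recruitment fell short of expectation early enough to change the cohort plan. A reader looks for the joining rate behind it and finds neither numerator nor denominator. A reader who asks how the barriers to joining were established finds no form or interview for women who were invited and did not come.

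Specific Aims describes the pilot as groundwork for an R21 application. Whoever plans that study needs an expected joining rate and the reasons women decline. The Results call the intervention feasible without giving either, and the Conclusions offer a forecast in their place. If stigma does keep women away, the women most affected are the ones the survey and class data cannot reach.

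**Working it through.** **1. The plan's own calculation.** The only design calculation is in Data Analysis: "We predicted with a sample size of 30, we would be able to detect medium effect sizes", with d = 0.53, alpha 0.05 and power 0.80. For a two-sided paired t-test on change scores, the degrees of freedom are 30 − 1 = 29 and the noncentrality is d√n = 0.53 × √30 = 2.90. Power is 0.801, so the figure reproduces. It concerns change among women who joined and says nothing about uptake.

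**2. What a statement about uptake needs.** Joining rate = number joined ÷ number invited.

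- Number invited: not given anywhere.
- Number eligible after screening on language, ethnicity and income: not given.
- Number joined: given as 30, beside a statement that fewer joined than expected.
- Number attending Class 1: not given by cohort or in total.

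Without a denominator, the only bound is that invited is at least joined. The rate could be any value up to 100%.

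**3. The two statements on enrolment.** Intervention Implementation says "each cohort of 10 participants participated in four two-hour classes held weekly", and the Research Timeline shows three cohorts: 3 × 10 = 30. If the two sequential cohorts replaced the three and kept that size, the total would be 2 × 10 = 20. Reaching 30 in two cohorts would need 15 in each. If they were added to the earlier cohorts, 30 could have been reached another way. The text does not say which happened, so the two statements cannot be reconciled from the document.

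**4. Sources that could support the forecast or the stated reasons.**

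| Source | Women covered | Demand or reasons for declining? |
|---|---|---|
| Survey, Class 1 and Class 6 | Attendees | No |
| Evaluation and feasibility items, follow-up only | Women reached at follow-up | No |
| Class audio and observation notes | Attendees | Not for women who stayed away |
| Case-management notes, action plans | Participants | Not for women who stayed away |
| Screening at recruitment | Women considered for entry | Eligibility only |
| Recruitment tracking | Not specified | Content not described; nothing reported |
| Team-meeting notes | Not specified | Possibly, as informal impressions |

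Data Analysis says that Aim 3 was judged from participants' perspectives. No row is described as measuring word of mouth or interest among women outside the study.

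**5. A side effect of the unclear count.** The same power calculation with assumed analysed numbers of 25, 20 and 15 gives detectable d of 0.58, 0.66 and 0.78, and power at d = 0.53 of 72%, 61% and 48%. These numbers are assumptions. They show only that the enrolment count matters beyond Aim 3.

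**The case against.** The strongest defence is that the document is candid. It discloses the shortfall and the cohort change, and presents the barriers to commitment as a limitation, so a planner sees the difficulty beside the optimistic sentence. The recruiter met these women in person and was well placed to hear why they hesitated. No effect estimate depends on the sentence. The document is largely retrospective, so a new recruitment log may come too late for this study. All of this stands. It limits the point to reporting and wording, but does not supply the missing counts.

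A reader might infer three stronger things that the documents do not support.

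- *That the shortfall contradicts the forecast.* The shortfall concerns early cohorts, while the forecast concerns uptake after word of mouth had spread. Both could be true.
- *That all the recruitment evidence is unfavourable.* The same paragraph says that 30 women, the planned number, were recruited and that women showed interest.
- *That nothing was collected on women who declined, or that the reasons have no source.* Screening and tracking took place, team-meeting notes were kept, and the reasons are credited to the recruitment process. The wording also need not refer only to women who stayed away; some may have hesitated and then joined. What is missing is a described record of reasons and any reported figure.

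**Conclusion.** The certainty claim is unsupported. It rests on word of mouth, which no described source measures, and on a recruitment record whose counts are not reported and whose two summary statements do not agree as written. The stated barriers are plausible, but on the evidence described they are the recruiter's impression.

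The point has no numerical size, because no joining rate can be formed from the document. Its practical weight is that a named Aim 3 measure goes unreported while a forecast stands in its place, in a pilot meant to inform the next application. The conclusion assumes that the recruitment tracking contains no record of reasons or demand beyond what the document describes. If it does, reporting it would settle the matter.

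**What to change.** **Now, in this document:**

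- From the tracked recruitment data, report women invited, eligible, joined and present at Class 1, by cohort, or state that these were not recorded.
- Reconcile the statement that 30 were recruited with the statement that fewer joined than anticipated, and say whether the two sequential cohorts replaced or followed the earlier ones.
- Replace the certainty sentence with the observed joining rate, or word it as a hypothesis for the next study.
- Label stigma, family and work obligations as the recruiter's impression, unless a record of reasons exists.

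**For any cohort still to be recruited, or the follow-on study:** keep one de-identified line per invited woman at the existing recruitment contact, recording eligible, interested, joined, and main reason for not joining.

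The cost is a little recording time, care that the log holds no identifiers for women who have not consented, and a less favourable sentence in the Conclusions.
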